• Positive and Negative Syndrome Scale (PANSS) (Kay et al. 1987), a rater-based scale used to assess and measure the severity of psychiatric symptoms over the past one week (unless previously obtained within the last one week)

The screening visit will take approximately two hours to complete and may be divided into separate sessions to minimize participant fatigue.

Research Laboratory Measures

Samples for these measures will be obtained at visit 2 (week 0), the start of the placebo run-in phase, and other time points as noted below.

- Blood sample (approximately 20 ml) to measure levels of immune markers and antibodies to infectious agents including high sensitivity CRP, TNF alpha, antibodies to food antigens such as casein and gliadin (Severance et al. 2012), and antibodies to NR2 (Dickerson, Stallings, Vaughan, Origoni, Khushalani, and Yolken 2012). Of note, CRP is a non-specific marker of inflammation which is elevated in many individuals with schizophrenia and has been found to be reduced by the administration of a sulforaphane nutraceutical (Bahadoran et al. 2013). These measures will also be performed at visit 7 (week 10) and visit 11 (week 18).
- Blood sample (approximately 8 ml) used to measure levels of biomarkers of inflammation including Keap 1/Nrf2-induced markers of cytoprotection and of the heat shock response (in peripheral blood mononuclear cells), using real time PCR and protein gels (Western blots). These samples will be analyzed in the Johns Hopkins Cullman Chemoprotection

- Center of [name]. These measures will also be performed at visit 7 (week 10) and visit 11 (week 18).
- Blood sample (4-6 ml) for the measurement of the blood level of the antipsychotic medication. These measures will be performed also at visit 11 (week 18).
- Throat swab samples for study of the oropharyngeal microbiome. These measures will be performed at visit 2 (week 0), visit 7 (week 10), and visit 11 (week 18)
- Urine sample for compliance and dose potency testing. Sulforaphane-glutathione dithiocarbamate (DTC) metabolites will be measured from urine provided by participants as biomarkers of compliance. These tests will also be performed at the Johns Hopkins Cullman Chemoprotection Center. These measures will also be performed at visit 7 (week 10) and visit 11 (week 18).

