These blood, throat swab, and urine samples will be identified by participant number only when they are sent to the research laboratories at Johns Hopkins for analysis. The clinical investigators will be blind to these results of the participant's research laboratory tests during the course of the trial. The laboratory scientists will be blind to the participant's treatment assignment during the course of the trial.

Placebo Lead-In Phase

Participants will begin a 2 week single-blind placebo phase at visit 2 (week 0), within 7 to 30 days of completion of the screening visit. Visit 2 (week 0) will take approximately two to three hours to complete. Participants who complete the two week placebo run-in phase and continue to meet eligibility criteria will be randomized to a treatment arm at visit 3 (week 2).

Randomization and Double-Blind Treatment Phase

Double-blind randomization will occur at visit 3 (week 2). Participants will be randomized to receive either the sulforaphane compound or placebo tablets which are indistinguishable from the sulforaphane tablets for the 16 weeks of the double-blind phase. Symptom evaluations will be completed at bi-weekly study visits at which time participants will also be evaluated for adverse events. Visits 3 to 10 (weeks 2 to 16) will take approximately one hour each to complete. Visit 11 (week 18) will take approximately two to three hours to complete.

Randomization will assure that out of N=64 total participants, approximately half are assigned to each treatment arm. In addition, block randomization, based on initial PANSS total scores, will be used to assign participants to the two treatment groups to avoid differences in initial PANSS scores between the groups. Only the study data manager and the study pharmacist will be aware of participant assignment during the trial.

Treatment providers will be asked to maintain participants on the same psychotropic medication regime throughout the study. At each bi-weekly study visit, research staff will document any medication changes. Any medication changes that are made will be studied as a secondary outcome.

The study compound will be taken once per day and the dose will not be adjusted throughout the trial.

Visit Windows

Visit 2 (week 0) will take place 7 to 30 days after visit 1 (screening). Visits 3 to 11 (weeks 2 to 18) will take place 12 to 16 days after the previous visit. Visits may be divided into separate sessions to minimize participant fatigue.

Compliance

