Pill counts and/or participant reports of compliance will be obtained. If pill counts or participant reports indicate the participant has not taken all of the prescribed study compound, the participant will be counseled about the importance of following directions. If the participant has missed more than 32 daily doses cumulatively throughout the study (>25% of study drug), the participant will be terminated from the study.

Compliance will also be confirmed with laboratory testing of urine samples provided by participants at 3 points during the trial (visits 2, 7, and 11). Participants will be told that these samples will be collected at random. These urine samples will be used to measure sulforaphane-glutathione metabolites in [name] laboratory.

Discontinuation

A participant may be discontinued from the study for any of the following reasons:

- If the participant fails to follow study directions (failure to keep appointments, follow directions or take the study compound as instructed)
- If the participant does not attend study visits, or is not in contact with research staff for 3 bi-weekly consecutive study visits
- If the participant has a positive drug screen, research staff will inform the participant that a repeat test will be done at the next visit; if the next test is positive then she/he will be removed from the study
- If it is the judgment of the study physician, in an effort to improve the participant's medical care, or if the participant develops a serious medical illness, becomes pregnant, or begins breast feeding
- If the participant has unexpected or serious side effects or serious medical complications

If a participant discontinues from the study, discontinuation assessments will be done at the discretion of the principal investigator.

A participant may withdraw from the study at any time at his/her own request.

Clinical Outcome Measures

• The primary outcome measurement will be the change in scores on the Positive and Negative Syndrome Scale (PANSS) (Kay et al. 1987) from the beginning to the end of the double-blind treatment phase, visits 3 to 11 (weeks 2 to 18). The PANSS contains 30 items that assess symptoms of schizophrenia including positive, negative and general symptom psychopathology. The PANSS was chosen because of its widespread use in clinical studies of psychosis and its demonstrated reliability in assessing psychopathology across diverse patient populations.

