7. STATISTICAL ANALYSIS

Power calculations indicate that a sample size of N=64 has 80% power to find an effect size of d = .76 with an alpha = .05 and a two-tailed test of change between groups from screening to end of study.

Aim 1: Safety data will be analyzed using incidence density analysis, to compare rates of adverse events across groups, as well as survival analysis, to assess group differences in retention. PANSS total scores will be the primary efficacy endpoint. Repeated-measures regression models will be used to assess the main effects of group and time, plus the time by group interaction. This method is able to utilize all available data from participants with

incomplete follow-up, thus including participants who drop out of the study. (Based on our experience in previous trials with this population, we anticipate attrition of about 15% over the course of the trial.) A similar analytical approach will be used for the PANSS subscales and the MCCB outcome measures.

Aim 2: Repeated measures regression modeling will also be used to evaluate the effect of medication group, time, and their interaction on inflammatory biomarkers.

Aim 3: Treatment groups will be compared with respect to initial and follow-up levels of inflammatory biomarkers using *t*-tests. If groups are found to differ in this regard, the efficacy analyses will be repeated, adding the initial biomarker levels as covariates in the model.

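### The power sentence covers a different interval from the primary outcome, and the efficacy model names no deciding contrast, baseline PANSS covariate or randomization-block term

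*Combined protocol and SAP*

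**What the plan says.** Section 5 (Clinical Outcome Measures) defines the primary outcome as PANSS change "from the beginning to the end of the double-blind treatment phase, visits 3 to 11 (weeks 2 to 18". Participants who finish the run-in and remain eligible "will be randomized to a treatment arm at visit 3 (week 2", so the outcome window opens at randomization.

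The power sentence in section 7 is for "a two-tailed test of change between groups from screening to end of study". It does not name the PANSS. The PANSS is the primary outcome, however, and in the section 9 schedule it is the only efficacy measure taken at screening; the MCCB and biomarkers start at week 0.

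For Aim 1, section 7 makes PANSS total the primary efficacy endpoint and adds: "Repeated-measures regression models will be used to assess the main effects of group and time, plus the time by group interaction". The only covariates mentioned anywhere in section 7 are initial biomarker levels, in a conditional repeat analysis under Aim 3.

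On allocation, section 5 says "block randomization, based on initial PANSS total scores, will be used to assign participants to the two treatment groups". Section 9 schedules the PANSS at screening, week 0 and week 2, and the plan does not say which of these is the initial score.

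**The concern.** Three gaps concern the same primary test.

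- The powered interval is not the outcome interval. It starts at screening and takes in the single-blind placebo phase.
- The model sentence lists effects without saying which one decides efficacy, how time is coded, or at which visit the arms are compared. The group main effect, an omnibus interaction, a slope and a week-18 contrast are different tests with different power. If none is named, the choice can be made after the data are seen.
- Randomization balances on PANSS, and up to three pre-randomization PANSS scores are collected, but the model names neither a baseline score nor the blocks. That gives up precision which is already paid for.

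**Working it through.** **1. The plan's own figure.** Inputs from section 7: N=64, d=.76, two-sided alpha .05, 15% attrition. Section 5 allocates about half to each arm. Completers: 64 × .85 = 54.4, about 27 per arm. For a two-sample t-test the noncentrality is d√(n/2).

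- 27 per arm: .76 × √13.5 = 2.79, 52 df, power 78.2% (79.7% by the normal approximation).
- 28 per arm: 79.8%.
- 32 per arm: .76 × √16 = 3.04, 62 df, power 84.9%.

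The 80% therefore reproduces as a comparison of one change score among roughly 54 completers. The power sentence does not say that attrition was allowed for.

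**2. The interval.** Section 5 (Visit Windows): "Visit 2 (week 0) will take place 7 to 30 days after visit 1 (screening" days and "Visits 3 to 11 (weeks 2 to 18) will take place 12 to 16 days after the previous visit". Screening thus precedes randomization by at least 7 + 12 = 19 days and at most 30 + 16 = 46. The screening PANSS itself can be older, since it is done "unless previously obtained within the last one week".

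The documents give no SD or correlation for either interval, so the effect on power cannot be computed, only illustrated. With equal SDs and the same raw effect, d=.76 on screening change becomes .76 × √[(1−r_s)/(1−r_b)] on week-2 change, where r_s and r_b are the correlations of the screening and week-2 scores with week 18. For assumed r_s=.4-.6 and r_b=.6-.7 this runs from .76 to 1.08, that is, 78% to 97% power with 27 per arm.

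**3. The possible deciding tests.** Assumptions: 27 completers per arm; d=.76 on week 2-18 change; week 2 to week 18 correlation r=.6 or .7; equal SDs; between-visit correlation constant, exponentially decaying, or a 50/50 mix; an effect growing linearly over the nine visits from week 2 to week 18. In SD units the week-18 effect is .76√(2(1−r)).

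Group main effect over nine visits: the average effect is half the final one. With constant correlation the SD of the nine-visit mean is √((1+8r)/9).

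- r=.6: .680/2 = .340; SD √(5.8/9) = .803; ratio .423; power 33%.
- r=.7: .589/2 = .294; SD √(6.6/9) = .856; ratio .344; power 24%.

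Over all three correlation patterns the range is about 20-33%. The other readings, on the same assumptions:

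| Test | Power, linear effect |
|---|---|
| Week-18 contrast in change from week 2 | 78% |
| 8-df interaction, F(8,45) | 39-70% |
| 8-df interaction, F(8,416) | 46-78% |
| GLS slope (no random slopes, so optimistic) | 78-96% |

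If half the effect is present at week 4 and all of it from week 6, the order changes: interaction 74-98% over both df choices, slope 68-79%, week-18 contrast still 78%.

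**4. Adjusting for week-2 PANSS.** Let s be the ratio of the week-2 SD to the week-18 SD. Adjusted variance divided by change-score variance is (1−r²)/(1+s²−2rs). The denominator exceeds the numerator by (s−r)², so in large samples adjustment never increases the variance, and it gains nothing when s=r. With s=1 the ratio is (1+r)/2. Power uses d = .76/√ratio with 51 df and 27 per arm; unadjusted power is 78.2%.

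| r | s=.8: ratio, power | s=1: ratio, power | s=1.2: ratio, power |
|---|---|---|---|
| .5 | .893, 83% | .75, 89% | .605, 94% |
| .7 | .981, 79% | .85, 84% | .671, 92% |
| .8 | 1.000, 78% | .90, 82% | .692, 91% |
| .9 | .950, 80% | .95, 80% | .679, 91% |

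**The case against.** The best defence is that section 5 already answers most of this. A change defined from visit 3 to visit 11, with PANSS total as endpoint and a model containing an interaction, points to the between-arm difference in change at week 18. That is the natural reading. But section 7 neither states it nor codes time, and its sentence gives the group main effect equal standing.

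Second, section 7 does not exclude visit 3 as a response, so week-2 PANSS may already be in the model. That is possible. With complete data and unconstrained means, however, the week-18-versus-week-2 interaction contrast is just the change-score difference, so the precision in step 4 is not recovered.

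Third, the completer benchmark is not the planned analysis, which uses all available data. This stands: with 32 per arm and the 15% loss spread evenly over visits (an assumption), the week-18 change contrast has about 81% power. The ranges in steps 3 and 4 likewise rest on assumed correlations, SD ratios and effect shapes.

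Several stronger readings are tempting and unsupported:

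- *The screening baseline biases the comparison.* It does not. Both baselines precede treatment, so randomization leaves the expected between-arm difference the same.
- *The 80% is wrong, or the trial is underpowered.* Step 1 reproduces the figure. In step 2 the same effect is no smaller in SD units on week-2 change under the assumed correlations.
- *Omitting baseline PANSS or the blocks causes bias.* It costs precision only.
- *Two tests at .05 push type I error to 1 − .95² = 9.75%.* Section 7 does not say that success on either term would suffice.

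**Conclusion.** The concern holds in a limited form. The stated power does not describe the defined outcome, the deciding contrast must be inferred from another section, and available baseline information is not named in the model. Validity and N=64 are not in question.

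The choice of contrast has the clearest consequence: a group main effect over all visits would have about 20-33% power for a linearly growing effect that the week-18 change contrast detects with 78%. The value of baseline adjustment is uncertain because the documents give neither r nor the SDs: 80-89% with equal SDs, 78-83% at an SD ratio of .8, and 91-94% at 1.2, for r from .5 to .9. No cost in power can be attached to the screening wording from the documents. This should be fixed before unblinding; it is not a reason to redesign the trial.

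**What to change.** - **Power sentence (section 7).** Restate it for PANSS change from week 2 to week 18 and say that it allows for 15% attrition.
- **Primary test (section 7).** Make the between-arm difference in PANSS total at week 18 the single primary test. Estimate it from the repeated-measures model with categorical visit and arm-by-visit terms, adjusted for visit-3 PANSS total. Report the group main effect and the omnibus interaction as supportive.
- **Blocking (section 5).** State which visit supplies the PANSS score used for blocking. Include the block term in the model unless that score is the visit-3 total already there.
- **Fallback.** Prespecify a simpler covariance in case the unstructured one does not converge. With eight post-randomization visits the unstructured form has 8 × 9/2 = 36 parameters. Baseline-by-visit terms may be reduced in a trial of 64.

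The cost is wording in section 7, one definition in section 5 and a few more model parameters. No new data, visits or patients are needed.

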5. STUDY DESIGN AND PROCEDURES

Study Overview

Over a two year period, we will randomize N=64 participants who have residual psychotic symptoms which are of at least moderate severity. Based on our experience performing similar clinical trials, we anticipate that we will evaluate up to 100 participants in order to randomize 64. We expect a drop-out rate of 15% after randomization. The trial will begin with a 2 week singleblind placebo run-in phase followed by a 16 week double-blind phase. During the placebo run-in phase, participants will receive placebo 6 tablets once per day. During the double-blind phase, participants will receive either the sulforaphane tablet 6 tablets once per day (equivalent to ~100 umol of sulforaphane) or the placebo 6 tablets once per day. The primary outcome that will be assessed is the severity of psychiatric symptoms as measured by the Positive and Negative Syndrome Scale (PANSS) (Kay et al. 1987). We will also measure cognitive functioning with the MATRICS Consensus Cognitive Battery (MCCB) (Nuechterlein et al. 2008). In addition, we will study the effect of the sulforaphane compound in lowering several biomarkers of inflammation including C-Reactive Protein (CRP), heat shock protein 90, and other markers of inflammation and cell damage. We will also investigate the association between the efficacy of sulforaphane therapy and initial and follow-up levels of these markers. For a detailed list of procedures and assessments at each study visit, see the Schedule of Assessments.

Study Compound

The active study compound and identical-appearing placebo will be prepared and provided by Nutramax Laboratories, Edgewood, MD, USA, the company that makes Avmacol®, a commercially-available over-the-counter compound (http://www.nutramaxstore.com/avmacolreg-60-tablets-p430.aspx). The active ingredient in Avmacol® is produced naturally by extracting the biologically inactive glucosinolate, glucoraphanin, from broccoli seeds, and compressing it in tablets with active myrosinase from broccoli sprouts. The ingestion of this compound leads to the

hydrolysis of glucoraphanin and the generation of sulforaphane within the gastrointestinal (GI) tract and the subsequent systemic absorption of the sulforaphane.

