• Secondary outcomes will be changes in scores on the MATRICS Consensus Cognitive Battery (MCCB) (Neuchterlein et al. 2008). The MCCB is comprised of 7 cognitive domains and 10 related tests (Trail Making Test: Part A; Brief Assessment in Cognition in Schizophrenia: Symbol Coding; Hopkins Verbal Learning Test-Revised; Wechsler Memory Scale-Third Ed: Spatial Span; Letter-Number Sequencing; Neuropsychological Assessment Battery: Mazes; Brief Visuospatial Memory Test-Revised; Category Fluency: Animal Naming; Mayer-Salovey-Caruso Emotional Intelligence Test: Managing Emotions; and Continuous Performance Test-Identical Pairs).

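### The MCCB is scheduled only at weeks 0 and 18, so the plan's repeated-measures model gains almost nothing from dropouts; comparing week 18 scores adjusted for baseline is a free improvement

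*Combined protocol and SAP*

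**What the plan says.** Section 7 (Aim 1) specifies regression models with group, time and their interaction for PANSS total. It gives as a merit that the method uses all data from participants with "incomplete follow-up, thus including participants who drop out of the study", and expects about 15% attrition. It then adds: "A similar analytical approach will be used for the PANSS subscales and the MCCB outcome measures".

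Section 5 (Clinical Outcome Measures) gives the MCCB its role: "Secondary outcomes will be changes in scores on the MATRICS Consensus Cognitive Battery (MCCB"). The schedule in section 9 marks the MCCB at visit 2 (week 0) and visit 11 (week 18) only. The PANSS is marked at every visit, and the blood markers of inflammation also have a week 10 sample. Section 5 places randomization at visit 3 (week 2), so the MCCB has one scheduled post-randomization measurement.

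For early leavers, section 5 (Discontinuation) says that "discontinuation assessments will be done at the discretion of the principal investigator". It names no instruments. The documents give no rule for a missing week 18 MCCB.

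**The concern.** The reason given for the model fits the PANSS. Someone who leaves at week 10 has already given several on-treatment ratings, and these inform the treatment effect. The same person has no on-treatment MCCB unless an exit battery happens to be done. Carrying the approach over without comment lets the MCCB result be read as protected against dropout when it rests almost wholly on those who reach week 18.

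The selection is not obviously harmless. Section 5 lists failure to take the study compound, a repeated positive drug screen, side effects and serious illness among the reasons for removal. All of these arise after randomization, and they could differ by arm or relate to cognition.

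There is also a question of efficiency. With only two time points, a group-by-time interaction is essentially a comparison of change scores. Adjusting the final score for the baseline score uses the same data more precisely.

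**Working it through.** **The plan's own figure.** Section 7 states that "a sample size of N=64 has 80% power to find an effect size of d = .76"; the significance level is two-sided 5%. With a two-sample comparison and unit SD, power is Φ(d·√(n/2) − 1.96) in the normal approximation.
- 32 per arm: 0.76 × √16 − 1.96 = 1.08, power 86.0% (84.9% by noncentral t).
- 28 per arm: 81.2% (79.8% by t).
- 27 per arm: 0.76 × √13.5 − 1.96 = 0.83, power 79.7% (78.2% by t).

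The stated 80% therefore fits about 54 to 56 participants analysed, not 64.

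**Inputs for the MCCB.** Section 5 gives 64 randomized, with "approximately half are assigned to each treatment arm", and 15% dropout after randomization. 64 × 0.15 = 9.6 leave and 54.4 remain. I take n = 32 randomized and m = 27 with a week 18 MCCB in each arm. The baseline-to-week-18 correlation r is not in the documents, so I show 0.5 to 0.9. Scores have unit SD at both visits, and dropout is taken as completely random, for the precision comparison only.

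**Standard error (SE) of the arm difference, in baseline SD units.**
- A. Change scores, completers only: √[2 × 2(1−r)/m].
- B. The plan's model (group, time, interaction) fitted by likelihood, with dropouts' baselines kept: √{2 × [(1−r²)/m + (1−r)²/n]}.
- C. Week 18 score adjusted for baseline, completers: √[2(1−r²)/m].
- D. Change scores if all 64 were measured: √[2 × 2(1−r)/n].

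| r | A | B | C | D | B below A | C below B |
|---|---|---|---|---|---|---|
| 0.5 | .272 | .267 | .236 | .250 | 2.0% | 12% |
| 0.7 | .211 | .208 | .194 | .194 | 1.2% | 7% |
| 0.8 | .172 | .171 | .163 | .158 | 0.8% | 4% |
| 0.9 | .122 | .121 | .119 | .112 | 0.4% | 2% |

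Example at r = 0.8: B = √{2 × [0.36/27 + 0.04/32]} = √0.02917 = .171; C = √(0.72/27) = .163.

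**What dropouts' baselines recover.** The share of the lost information regained, (A² − B²)/(A² − D²), equals (1−r)/2: 25% at r = 0.5, 10% at 0.8 and 5% at 0.9.

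**Small-sample check on C.** The formulas treat the baseline slope as known. Simulation with the slope estimated (100,000 runs per value of r) gave B and C of .267 and .238, .209 and .197, .171 and .164, .122 and .120. The gain of C over B is then 11%, 6%, 4% and 1%. It is slightly smaller than by formula, but C remains the more precise at every correlation tried.

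**The case against.** The strongest reply is that nothing in section 7 is false. A likelihood model with week 0 as a response does keep dropouts' baseline scores. The sentence about dropouts was written for the PANSS, and the MCCB is promised only a similar approach. The discontinuation rule allows an exit MCCB. The plan also intends a survival analysis of retention by group, which would reveal differential dropout. All of this stands. A reader might infer that dropouts cannot be scored, or that the statement on dropouts is simply wrong for the MCCB; the documents support neither. They support less: an exit MCCB is permitted but not secured, and the baselines that are kept add very little. If change scores were analysed, as the definition of the outcome suggests, dropouts without a later score would be left out altogether; the plan does not say which form applies. The retention analysis would flag a problem but not address it in the MCCB result.

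A second reply is that the outcome is secondary, that about 10 participants are affected, and that the choice of missing-data method is partly preference. That also stands as far as imputation goes. One might be tempted to impute week 18 MCCB within arm from every PANSS rating. That would mean up to 11 ratings fitted on about 27 completers, with no PANSS–MCCB correlation in the documents to suggest a gain. I do not ask for it.

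**Conclusion.** The point holds in a limited form. For the MCCB, the plan's model is in effect a change-score comparison among about 54 completers, and the dropout rationale has little force: dropouts' baselines lower the standard error by about 0.4% to 2%. Adjusting week 18 MCCB for visit 2 MCCB lowers it by about 2% to 12% by the large-sample formulas, or about 1% to 11% with the slope estimated. These figures rest on 15% attrition split evenly, equal variances at the two visits, and correlations of 0.9 to 0.5, which are assumed.

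Two stronger conclusions should not be drawn. A reader might infer that the trial is underpowered for the MCCB. The stated effect size already fits about 27 to 28 per arm, and it is not said to be for the MCCB, so no shortfall against the plan's figure is shown. A reader might also infer a bias of known size. The documents say nothing about how the arm difference among dropouts compares with that among completers, so any such number would be invented. Bias is possible, and that is the reason for a sensitivity analysis. I class this as a free improvement, not an error in the plan.

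**What to change.** In section 7 (Aim 1), keep the carry-over sentence for the PANSS subscales and replace it for the MCCB with wording such as: *Week 18 MCCB will be compared between arms adjusting for visit 2 MCCB.* Then make three small additions.

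1. Limit the statement that dropouts are included to outcomes with repeated post-randomization ratings.
2. Report by arm the number with an observed week 18 MCCB (about 54 expected in total), and say whether the MCCB is part of any discontinuation assessment.
3. Add one delta-shift sensitivity analysis: missing week 18 scores are predicted from arm and visit 2 MCCB, then shifted over a range fixed before unblinding, to show how far the conclusion depends on them.

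The cost is a few sentences and a little analysis. No visit, test or participant is added. The one drawback is presentational: the MCCB result must be described as resting on those observed at week 18.

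### Aim 2 does not adjust each inflammatory marker for its own pre-randomization week 0 value, so its planned tests are valid but less precise than the data allow

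*Combined protocol and SAP*

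**What the plan says.** **Timing.** On the research laboratory measures, section 5 states: "Samples for these measures will be obtained at visit 2 (week 0), the start of the placebo run-in phase, and other time points as noted". The inflammatory and cytoprotection markers are repeated at visit 7 (week 10) and visit 11 (week 18), and the Schedule of Assessments in section 9 agrees. Randomization is at visit 3 (week 2), after a two-week run-in in which everyone takes placebo. The week 0 marker is therefore a true pre-randomization baseline.

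**Aim 2 (section 7).** "Repeated measures regression modeling will also be used to evaluate the effect of medication group, time, and their interaction on inflammatory biomarkers". The text does not list the time points. It does not say whether week 0 is a response or a covariate, and it does not name the contrast or visit that answers the aim.

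**Aim 3 (section 7).** "Treatment groups will be compared with respect to initial and follow-up levels of inflammatory biomarkers using" (the test named is the t-test). Should a difference be found, the efficacy models are to be refitted with the initial marker levels added. That is the only place where an initial marker level serves as a covariate, and the outcome there is efficacy, not the marker.

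**Power (section 7).** The single statement is that "a sample size of N=64 has 80% power to find an effect size of d = .76"; it refers to a two-sided comparison of change at the 5% level. No effect size, standard deviation, within-person correlation or power is given for any marker.

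**The concern.** Because the week 0 sample precedes randomization, any difference between arms at that visit is chance. A model with group, time and their interaction, fitted to weeks 0, 10 and 18, nevertheless estimates a free arm difference at week 0. This has two consequences.

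- The interaction becomes a comparison of change from week 0. It subtracts the whole baseline value, although only a fraction of it, equal to the correlation, predicts the follow-up value.
- The group effect averaged over the three visits mixes two visits at which an effect may exist with one at which it cannot.

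Aim 2 asks whether the compound lowers inflammatory markers. The trial is small, with 64 randomized and about 15% attrition expected. Giving up precision that the scheduled samples already provide makes it more likely that a real marker effect is missed.

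**Working it through.** **1. The plan's own figure.** Inputs from the documents: 64 randomized, "approximately half are assigned to each treatment arm", attrition 15%, d = 0.76, two-sided alpha 0.05. Normal approximation: power = Φ(d·√(n/2) − 1.96), with n per arm.

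- n = 32 (no attrition): 0.76 × √16 = 3.04; Φ(1.08) = 86.0%.
- n = 64 × 0.85 / 2 = 27.2: 0.76 × √13.6 = 2.803; Φ(0.843) = 80.0%.

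The stated 80% is reproduced once attrition is applied. The figure is not tied to any marker. It serves below only to set the scale.

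**2. Variances at week 18.** Assumptions, not in the documents: equal marker variance at each visit and a common correlation ρ between visits. In units of 2σ²/n:

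- change from week 0: 1 + 1 − 2ρ = 2(1 − ρ)
- adjusted for week 0: 1 − ρ²
- ratio, adjusted to change: (1 − ρ²) / [2(1 − ρ)] = (1 + ρ)/2

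The ratio is below 1 for every ρ below 1, so under these assumptions the direction of the result does not depend on the missing correlation. Only the size does.

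**3. Power regained at week 18.** With 54 analysed (64 × 0.85 = 54.4), the change contrast has 52 degrees of freedom, and a noncentrality of 2.855 gives it 80% power. Dividing by √((1 + ρ)/2) and reading the noncentral t with 51 degrees of freedom gives:

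| Assumed ρ | Variance ratio | Noncentrality | Power, adjusted |
|---|---|---|---|
| 0.3 | 0.65 | 3.541 | 93.5% |
| 0.5 | 0.75 | 3.296 | 89.9% |
| 0.7 | 0.85 | 3.096 | 85.9% |
| 0.8 | 0.90 | 3.009 | 83.9% |

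Each row fixes the change contrast at 80%, so each row refers to a different raw effect.

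**4. Same raw effect in every row.** Assume a marker effect of 0.76 SD at both follow-ups, 27 per arm, normal approximation. The group effect averaged over three visits has expected value (0 + 0.76 + 0.76)/3 = 0.507 SD, which is 2/3 of the follow-up effect, and variance (1 + 2ρ)/3 in the same units. The interaction, with time categorical, is a 2-df test.

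| Assumed ρ | Change, week 18 | Interaction, 2 df | Group effect over 3 visits | Adjusted, week 18 |
|---|---|---|---|---|
| 0.3 | 65.5% | 68.3% | 72.2% | 83.3% |
| 0.5 | 79.7% | 83.1% | 62.6% | 89.7% |
| 0.7 | 95.0% | 96.9% | 54.8% | 97.4% |
| 0.8 | 99.3% | 99.7% | 51.6% | 99.6% |

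The group effect over three visits loses power as ρ rises, whereas the adjusted contrast gains. Against the 2-df interaction, the adjusted week 18 contrast gains 15 points at ρ = 0.3, 7 points at 0.5, and almost nothing at 0.7 or above.

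**The case against.** **The model structure is inferred.** The plan never says that week 0 is a response. This stands. It is the natural reading, because the markers have only three visits and no covariate is named. If the sponsor intends week 0 as a covariate, the change needed is only to say so.

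**The gain may be small.** This stands too. If the markers are strongly correlated within person, the planned interaction loses little, and the documents give no correlation for any marker. The group effect over three visits is the exception: there the loss grows with the correlation.

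**Nothing here is biased.** Correct. Under randomization the change contrast is unbiased and its test holds its error rate. The averaged group effect also gives a valid test of no effect, although its estimate is diluted.

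**54 is not the planned analysis set.** Section 7 says that repeated-measures regression uses all available data, and Aim 2 uses the same approach. Someone lost after week 10 still contributes. The 54 is a simplification; the variance ratios do not depend on it.

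**Two stronger readings are tempting, and the documents do not support them.** A reader might infer that the collected baseline goes unused. It does not: if week 0 is a response, the interaction uses it as change, and Aim 3 tests initial levels and may add them to the efficacy models. A reader might also infer that the Aim 3 follow-up t-tests are a second, underpowered estimate of the marker effect. Aim 3 concerns the association between efficacy and marker levels. In section 7 its t-tests serve to decide whether the efficacy models are refitted; estimating the marker effect is left to Aim 2.

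**Conclusion.** The point holds for Aim 2 as a loss of precision, not as an error. No text adjusts a marker for its own week 0 value, and on the natural reading both planned tests use that value inefficiently. At week 18 the adjusted variance is (1 + ρ)/2 of the change-contrast variance. An 80% power would become about 93%, 90%, 86% and 84% at ρ = 0.3, 0.5, 0.7 and 0.8. These figures rest on equal variances, a common correlation, 54 analysed and values of ρ that are assumed. If the group effect over three visits were taken as the answer to Aim 2, it would target 2/3 of the follow-up effect, with 72% to 52% power over the same range for an assumed 0.76 SD effect.

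This is a worthwhile improvement to a secondary aim. The primary PANSS analysis, its sample size and the Aim 3 t-tests are not affected.

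**What to change.** In section 7, Aim 2, replace the model sentence with one that states:

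- the responses are each marker at weeks 10 and 18;
- the terms are group, visit, group-by-visit and the week 0 value of the same marker; or, equally acceptable, week 0 stays a response with the arm means constrained to be equal there;
- the Aim 2 result is the adjusted group difference at week 18.

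Naming the contrast also settles which of the group effect and the interaction answers the aim, which the present text leaves open.

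Cost: wording only, since the week 0 samples are already scheduled for everyone. The covariate form uses one degree of freedom per marker and loses participants without a week 0 value. The constrained form keeps those participants, so it is preferable if many week 0 samples are missing. Aim 3 needs no change on this ground.
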